7.2. Screening

The pre-screening can be performed via REDCap (questions 1, 2, 3, 4); the whole screening (questions 1-12) is performed via telephone. Result of the screening procedure: eligible or not eligible.

The following questions will be asked:

1. Are you at least fifty years old? If not, then not eligible.
2. Do you have an implanted device or metal in your head (including a cochlear implant), or do you have hearing aids? If yes, then not eligible.
3. Do you have a cardiac pacemaker? If yes, then not eligible.
4. Alcohol Use Disorders Identification Test (AUDIT) 1-3: Gender: Woman / man / transgender / non-binary / prefer not to respond. Age: <65 years / ≥65 years? How often do you have a drink containing alcohol? How many drinks containing alcohol do you have on a typical day when you are drinking? How often do you have 4 (for females) or 5 (for males) – or more – drinks on one occasion? Cutoff (i.e. not eligible): ≥7 for females and for males ≥ 65 years; ≥8 for males <65 years.
5. Are you willing to abstain alcohol at least 24 hours before each study visit? If no, then not eligible.
6. Have you ever been told by a healthcare provider that you have one of the following neurologic diseases: Epilepsy, sleep disorder (insomnia, sleep apnea, restless legs syndrome, parasomnia), stroke or transitory ischemic attack, cognitive impairment, neurodegenerative disease (for example Alzheimer's disease, Parkinson's disease or amyotrophic lateral sclerosis), immune-mediated disease of the central nervous system, chronic infectious brain disease, brain tumor, traumatic brain injury with loss of consciousness and/or intracranial bleeding, chronic pain with the need for daily analgesic use? If yes, then not eligible.
7. Did you ever have brain surgery? If yes, then not eligible.
8. Have you been told by a healthcare provider that you have one of the following psychiatric diseases (in your lifetime or during the last three months): Schizophrenia (in your lifetime), obsessive compulsive disorder (OCD; in your lifetime), borderline personality disorder (in your lifetime), anxiety disorder (in your lifetime), bipolar disorder (in your lifetime), psychosis (in your lifetime), eating disorder (in your lifetime), depression (during the last three months)? If yes, then not eligible.
9. Have you ever been told by a healthcare professional that you have one of the following medical conditions: Moderate to severe chronic obstructive pulmonary disease (COPD), abnormal kidney function (defined as estimated Glomerular Filtration Rate <60ml/min), current liver disease (defined as hepatitis and/or liver cirrhosis), cancer, diabetes mellitus, cardiac disease (heart failure, myocardial infarct, atrial fibrillation and revascularization – all within the last three months)? If yes, then not eligible.
10. Do you work night shifts (last three months)? If yes, then not eligible.
11. Do you usually go to bed after midnight (last three months)? If yes, then not eligible.
12. Have you used psychotropic treatment or illegal drugs (including cannabis) within the last three months? If yes, then not eligible.

If online pre-screening is successfully completed and the participant appears eligible, the following message will appear: Please leave name, email, phone number and preferred time to be called by phone.

The following information will be provided by telephone:

1. A brief summary of the study and its objectives.
2. Instructions for the meeting at the lab:
 - 2.1 In the 24 hours before the visit: Please do not drink alcohol and do not drink more caffeine than you usually do.
 - 2.2 Please bring a list of all medications you regularly take (including those not prescribed by a healthcare professional).

If not yet the case, the online questions will be completed by phone.

There may be up to 28 days between (pre-)screening and enrollment.

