4.3. Measurement Design

Table 1. Variables of interest: their occasions of evaluation, their uses for the aims, their roles in the study

| Variables within Domains | Scale ¹ | Occasions ² | Aims ³ | Main Roles |
|---|---------------------|------------------------|-------------------|---------------------------|
| Identifiers | | | | |
| Participant's unique ID | Nominal | All | All | Identifier |
| Intervention (A or B)* | Binary | E | All | Identifier |
| General Profile | | | | |
| Age | Decimal yrs | S | All | Screening, covariate uses |
| Implanted device/hearing aid | Binary | S | All | Screening |
| Cardiac pacemaker | Binary | S | All | Screening |
| Willingness to abstain from alcohol ≥24h before visit | Binary | S | All | Screening |
| Known neurologic diseases | Binary | S | All | Screening |
| Known psychiatric diseases | Binary | S | All | Screening |
| Known other medical conditions | Binary | S | All | Screening |
| Brain surgery in the past | Binary | S | All | Screening |
| Night shifts, bed after midnight | Binary | S | All | Screening |
| Use of illegal drugs | Binary | S | All | Screening |
| Sex | Categorical | 0 | All | Covariate uses |
| Racial/ethnic categories | Categorical | 0 | All | Covariate uses |
| Education | Categorical | 0 | All | Covariate uses |
| Living conditions | Categorical | 0 | All | Covariate uses |
| Work status | Categorical | 0 | All | Covariate uses |
| Clubs/social organizations | Binary | 0 | All | Covariate uses |
| Sports | Binary, categorical | 0 | All | Covariate uses |
| Social contacts | Binary, categorical | 0 | All | Covariate uses |
| Media consumption | Categorical | 0 | All | Covariate uses |
| Concomitant medications list | Nominal | 0 | All | Covariate uses |

| | | | | |
|--|---|----------------------------|--------------|--|
| Caffeine consumption | Binary, nominal, dL | 0 | All | Covariate uses |
| Alcohol consumption | Binary, nominal, dL | 0 | All | Covariate uses |
| Smoker | Binary, yrs, cig/d | 0 | All | Covariate uses |
| Questionnaires | | | | |
| Sleep Quality Assessment PSQI (15) | Ordinal 0-21 | 0 | All | Screening |
| Patient Health Questionnaire-9 (16) | Ordinal 0-27 | 0 | All | Screening |
| General Anxiety Disorder-7 (17) | Ordinal 0-21 | 0 | All | Screening |
| Alcohol Use Disorders Identification Test (1-3) (18) | Ordinal 0-18 | S | All | Screening |
| AD8 Dementia Screening (19) | Ordinal 0-8 | 0 | All | Screening |

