5.2.1. Exclusion Criteria

Any individual who meets one or more of the following criteria will be excluded from participation:

- Implanted device or metal in head (including cochlear implant or other hearing aid), cardiac pacemaker or any other powered medical device
- Known neurological disease from history (epilepsy, sleep disorder (insomnia, sleep apnea, restless legs syndrome, parasomnia), stroke or transitory ischemic attack, cognitive impairment, neurodegenerative disease (for example Alzheimer's disease, Parkinson's disease or amyotrophic lateral sclerosis), immune-mediated disease of the central nervous system, chronic infectious brain disease, brain tumor, traumatic brain injury with loss of consciousness and/or intracranial bleeding, chronic pain with the need for daily analgesic use)
- Positive screening for epilepsy (questionnaire)
- Pathological Montreal Cognitive Assessment (MoCA $<26/30$ points)
- Brain surgery in the past (lifetime)
- Known psychiatric disorder from history (schizophrenia (lifetime), obsessive compulsive disorder (OCD; lifetime), borderline personality disorder (lifetime), anxiety disorder (lifetime), bipolar disorder (lifetime), psychosis (lifetime), eating disorder (lifetime), depression (within the last three months))
- Positive screening for anxiety disorder (GAD-7 $\geq 10/21$ points) or positive screening for depression (PHQ-9 $\geq 5/27$ points)
- Known other relevant medical condition from history (moderate to severe chronic obstructive pulmonary disease (COPD), abnormal kidney function (defined as estimated Glomerular Filtration Rate $<60\text{ml}/\text{min}$), current liver disease (defined as hepatitis and/or liver cirrhosis), cancer, diabetes mellitus, cardiac disease (heart failure, myocardial infarct, atrial fibrillation and revascularization – all within the last three months))
- Working in night shifts or going to bed after midnight on 3 or more nights per week
- Positive screening for sleep disorder (PSQI $>5/21$ points)

- Psychotropic treatment or illegal drugs (including cannabis) within the last three months
- Indication for alcohol use disorder: AUDIT score (Alcohol Use Disorders Identification Test; screening for unhealthy alcohol use) ≥ 7 for females and for males ≥ 65 years or ≥ 8 for males <65 years
- Not willing to abstain alcohol at least 24 hours before each study visit
- Women who want to become pregnant, are pregnant, plant to seek or are seeking fertility treatment

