5.3.2. Screen Failures

In the case that a participant enrolls in the trial and the screening reveals that they do not meet study criteria, the study personnel completing the interviewing process will clearly explain why the participant does not meet criteria. If a time-sensitive criterion is not met, re-screening may occur at a later time. In the worst case, we expect only $\sim 25\%$ of those interested to be eligible.

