7.1. Table of Events

| Procedure | | Visit 0 screening (online/phone) | Visit 1 Baseline (from day after Visit 0 to +14 days) | Visit 2 (day after Visit 1) | Visit 3 (day after Visit 2) | Visit 4 (telephone; 5 days after Visit 2) | Visit 5 (6-9 days after Visit 2) | Visit 6 (day after Visit 5) | Visit 7 (telephone; 5 days after Visit 5) |
|--------------------------|---|----------------------------------|---|-----------------------------|-----------------------------|---|----------------------------------|-----------------------------|--|
| Recruitment | Informed consent | X (oral) | X (written) | | | | | | |
| | Eligibility assessments | X | X | | | | | | |
| | Enrollment and randomization | | X | | | | | | |
| Eligibility assessments | At least 4 hours of initial sleep-EEG | | | x | | | | | |
| | No epileptiform discharges in baseline-EEG | | x | | | | x | | |
| | No psychotropic treatment/illegal drugs within the last 3 months, no alcohol within the last 24 hours | | | x | x | | x | x | |
| Intervention | (Control) Stimulation | | | x | | | x | | |
| | Cognitive testing ¹ | | | x | x | x (only verbal memory and associative verbal memory recall) | x | x | x (only verbal and associative verbal memory recall) |
| | Sleep-EEG ² | | x (next night) | x (next night) | | | x (next night) | | |
| | Actigraphy | | x | x | x | x | x | x | |
| | TMS Motor Thresholding | | | x | | | | | |
| Patient Reported Outcome | Subjective tolerability of sleep EEG | | | x | x | | | x | |
| | Sleepiness (Karolinska Scale) | | | x | x | | x | x | |
| | Sleep quality | | | x | x | | x | x | |
| | Affect (PANAS) | | | x | x | | x | x | |
| Safety Monitoring | Assessment of AEs | | | x | x | x | x | x | x |

¹ Standardized results of: RAVLT (Rey Auditory Verbal Learning Test) (26), word association test, Letter Fluency (28), Stroop Color and Word Test (29), Trail Making Test A and B (30), TAP (Test of Attentional Performance) (31).

² Device worn (yes/no), hours of recording, sleep latency, sleep efficiency, amount of sleep spindles and slow wave sleep.

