7.5. Early Discontinuations

Data to be Collected

If the study participation has to be terminated early by the investigators (due to safety concerns), or if a participant chooses to withdraw from the study, including the case of not showing up for scheduled visits on site (Visits 1, 2, 3, 5, 6), the data collected to date will not be included for the cognitive and sleep-EEG outcomes and the participant will be replaced. However, early discontinuation will be included in the data set for the feasibility outcomes as appropriate. Visits 4 and 7 are not mandatory for study completion.

Criteria for Intervention Discontinuation

An investigator may discontinue or withdraw a participant from the study for the following reasons:

- Any clinical adverse event (AE), intercurrent illness or other medical condition, or situation occurs such that continued participation in the study would not be in the best interest of the participant.

- The participant meets any exclusion criteria (either newly developed or not previously recognized) or a reason for immediate early termination of participation.

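### The phone screen asks about a cardiac pacemaker, but no listed question asks about the other powered devices that section 5.2.1 excludes

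*Combined protocol and SAP*

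**What the plan says.** Section 5.2.1 (Exclusion Criteria) and the synopsis use the same device criterion. It covers an implanted device or metal in the head, including cochlear implants and hearing aids, and then a "cardiac pacemaker or any other powered medical device".

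Section 7.2 lists twelve screening questions and describes these as the whole telephone screen, which ends in a result of eligible or not eligible. Two of them concern devices. Question 2 asks: "Do you have an implanted device or metal in your head (including a cochlear implant), or do you have hearing aids". Question 3 asks: "Do you have a cardiac pacemaker? If yes, then not eligible".

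Table 1 (section 4.3) has two device variables, both collected at screening: "Implanted device/hearing aid" and "Cardiac pacemaker".

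The plan also contains more general safeguards:
- Section 4 says that a site visit is arranged once the criteria are met in the phone screen.
- The Table of Events (section 7.1) marks eligibility assessments at Visits 0 and 1.
- Section 12.1 says that contraindications are screened by phone before the TMS session.
- Sections 5.3.2 and 7.5 deal with people who are found ineligible after enrolment.

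**The concern.** The script is where eligibility is first decided and recorded, and it is narrower than the criterion it is meant to apply. A person who wears a powered device, and whose diagnosis is not among those asked about, can answer all twelve questions truthfully, be recorded as eligible, and still meet a written exclusion. TMS motor thresholding and tACS both follow at Visit 2.

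Section 2.2 says that the exclusion criteria are also meant to remove contraindications to tACS. A device exclusion serves that purpose only if someone asks about the device. What is at stake is participant safety and correct application of the eligibility criteria, not the analysis.

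**Working it through.** No arithmetic applies. The check sets each part of the device criterion in section 5.2.1 against the two device questions in section 7.2.

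| Part of the criterion | Where it is asked | Covered? |
|---|---|---|
| Implant or metal in the head | Question 2 | Yes |
| Cochlear implant, hearing aid | Question 2 | Yes |
| Cardiac pacemaker | Question 3 | Yes |
| Other powered device, implanted outside the head | Question 2, only if its first words are read as any implant anywhere in the body | Depends on the reading |
| Other powered device, worn or external (other than a hearing aid) | Nowhere | No |

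**The two readings of question 2.** On the generous reading, an implanted device means one anywhere in the body. The Table 1 label "Implanted device/hearing aid" does not mention the head and allows this. On the narrower reading, the reference to the head governs both the device and the metal. The structure of the script favours the narrower reading: a pacemaker is itself an implant, so question 3 would be redundant if question 2 already covered every implant. That is an inference, not proof. The worn or external devices in the last row are missed either way.

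**Indirect capture through diagnoses.** Question 6 removes people with epilepsy, Parkinson's disease, sleep apnea, or chronic pain needing daily analgesics. Question 9 removes people with diabetes. Some device users will be caught in this way, but not all. An implanted defibrillator illustrates the narrower reading: question 9 limits its cardiac conditions to the last three months, so someone with an older history could pass.

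**Later listed steps before first stimulation.** The Visit 0 and 1 procedures in section 7.3 cover consent, demographics and medications, screening and profile questionnaires, instructions and randomization. Visit 2 then asks about alcohol and drugs, sleep quality, sleepiness and mood before TMS thresholding, tACS amplitude thresholding and stimulation. None of these items names a device. Visit 5 includes a question on new diagnoses, but it comes after the first stimulation session.

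**The case against.** The strongest reply is that the script is not the only control. Section 4 makes the site visit conditional on the criteria being met by phone. Section 7.1 repeats the eligibility assessment at Visit 1 ("Eligibility assessments | X | X" for Visits 0 and 1). Section 12.1 describes a phone screen for TMS contraindications and says that these are well documented in the field. Trained staff who apply those statements would probably ask about other devices.

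The section 7.3 list is also plainly incomplete. It omits the baseline EEG that section 7.1 places at Visit 1, and its heading for the screening questionnaires names epilepsy without listing an epilepsy instrument. The absence of a device item from that list is therefore weak evidence that none will be asked.

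Much of this stands. A reader might infer that the plan has no safeguard, or that people with powered devices will be stimulated. The documents do not support either reading. A reader might also infer that most of the device criterion goes unasked, but questions 2 and 3 cover head devices, hearing aids and pacemakers.

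What the reply does not do is supply the missing prompt. The general statements name no device item. The section 12.1 text is framed around traits that raise seizure risk, and it points back to the phone screen whose questions section 7.2 sets out in full. Section 5.3.2 ("In the case that a participant enrolls in the trial and the screening reveals that they do not meet study criteria") and the withdrawal rule in section 7.5 help only once someone has recognized the problem.

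**Conclusion.** The mismatch is real and minor. The written criterion excludes all powered medical devices, while the script and Table 1 ask only about some of them. Worn or external devices other than hearing aids are unasked on any reading. Implants outside the head other than a pacemaker are unasked on the narrower reading of question 2. Whether such a person is identified before TMS and tACS depends on staff applying the full criterion without a listed prompt.

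The documents give no prevalence of such devices in this population, so the number affected cannot be estimated. With enrolment capped at 50 and several device-related diagnoses already excluded, it is probably small. The conclusion assumes that the questions are asked as printed in section 7.2. If a separate contraindication checklist with a device item is in use, the practical risk largely disappears and only the wording needs aligning. No estimate, test or sample size calculation is affected.

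**What to change.** Extend question 3 in section 7.2, and the Table 1 row "Cardiac pacemaker", to the wording of section 5.2.1, "cardiac pacemaker or any other powered medical device", with the words *implanted or worn* added. This closes the gap on both readings of question 2.

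The exclusion for pregnancy, planned pregnancy and fertility treatment in section 5.2.1 also has no matching screening question. One could be added in the same revision of the script, although it is a separate matter.

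The cost is IRB review of the revised script and possibly a few more screen-outs. No new procedure or visit is needed.

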7.3. Enrollment

Visits 0 and 1

The following procedures will occur:

1. Signing of informed consent
2. Completion of demographics and supplementary questions (mainly providing information about the cognitive state): Sex, racial/ethnic categories, education, living conditions, work status, clubs/social organizations, sports, social contacts, media consumption, concomitant medications list, caffeine consumption, alcohol consumption, smoking status.
3. Specific questionnaires to exclude patients with indications for a sleep disorder, depression, anxiety disorder, cognitive impairment, epilepsy:
 - 3.1 Sleep Quality Assessment PSQI (15): Screening for sleep disorders. Result: 0-21 points. Exclusion if >5 points.
 - 3.2 Patient Health Questionnaire-9 (16): Screening for depression. Result: 0-27 points. Exclusion if ≥5 points.
 - 3.3. General Anxiety Disorder-7 (17): Screening for anxiety disorder. Result: 0-21 points. Exclusion if ≥10 points.
 - 3.4. Montreal Cognitive Assessment (MoCA): Screening for dementia. Result: 0-30. Exclusion if <26.
4. Complementary questionnaires to complete patient profile:
 - 4.1 Handedness Questionnaire (22)
 - 4.2 Behavioral Inhibition and Behavioral Activation Self Report Scales (BIS/BAS) (23): These scales are used to monitor the perceived sensitivity to reward and punishment. BIS/BAS is broken into four sub-scores: BIS (7 to 28), BAS drive (4-16), BAS fun-seeking (4-16), and BAS reward (7-20).
 - 4.3 Basic sleep habits (bedtime, sleep latency, wakefulness during the night, waking time, total amount of sleep on average, optimal total amount of sleep)
5. The following instructions will be given for the night and following day:
 - 851 How to use the EEG-headband the night before visit 2 (oral and written instructions, including sleep diary); how to use the actigraphy watch.
 - 5.2 To not consume more caffeine than usually. To please not drink alcohol.
6. The participant will be randomized to the respective intervention for visit 2 (either gamma-tACS or first control stimulation).

7.4. Study Visits

Visit 2 (day after Visit 1; afternoon/early evening, i.e. start between 12pm and 6pm)

1. Questioning whether there has been any use of alcohol, psychotropic substances or illicit drugs during the past 24 hours. If yes, study participation is terminated.
2. Questions to assess current sleepiness and mood, as this may affect the results of further testing:
 - 2.1 Questions for sleep quality the night before
 - 2.2 Karolinska Sleepiness Scale (24)
 - 2.3 Positive And Negative Affect Schedule (PANAS) (25)
3. Motor thresholding by TMS.
4. Thresholding individual tACS amplitude.
5. Gamma-tACS or control stimulation (according to randomization) during the following cognitive tests, presented on a computer screen (2 minutes of resting EEG without stimulation after each test; total duration approximately 40 minutes):
 - 5.1 Rey Auditory Verbal Learning Test (RAVLT, version 1) (26)
 - 5.2 Letter Fluency; letters F, A, S (28)
 - 5.3 Stroop Color and Word Test (29)
 - 5.4 Trail Making Test A and B (30)

- 5.5 Word association test; version 1
- 5.6 Four subtests of the Test of Attentional Performance (TAP) (31): Alertness, Go/Nogo, Divided Attention, Visual Scanning
- 5.7 RAVLT delayed recall
6. Evaluation of side effects with open question (“Did you feel anything particular or note anything special during this session?”)
7. The participant will be given the sleep diary for the second night with the EEG headband.

Visit 3 (day after Visit 2; morning, i.e. start between 8am and 12pm)

1. Questioning whether there has been any use of alcohol, psychotropic substances or illicit drugs during the past 24 hours. If yes, the participant is excluded.
2. Questions to assess current sleepiness and mood, as this may affect the results of further testing:
 - 3.1 Questions for sleep quality the night before
 - 3.2 Karolinska Sleepiness Scale
 - 3.3 Positive And Negative Affect Schedule (PANAS)
3. Cognitive follow-up testing
 - 4.1 RAVLT “ultra-delayed” recall; version 1
 - 4.2 Letter fluency; letters B, H, R
 - 4.3 Stroop Color and Word Test (SCWT)
 - 4.4 Trail Making Test Part A and B
 - 4.5 Word association recall; version 1
 - 4.6 Four subtests of the Test of Attentional Performance (TAP): Alertness, Go/NoGo, Divided Attention, Visual Scanning

Visit 4 (telephone; 5 days after Visit 2)

Performed by telephone.

1. Assessment of adverse events.
2. RAVLT “ultra-delayed” recall; version 1.
3. Word association recall; version 1.

Visit 5 (6-9 days after Visit 2; afternoon/early evening, i.e. start between 12pm and 6pm)

The day before: reminder (e-mail/SMS/phone call, depending on the participant's preference) of appointment on the following day - including request to abstain from alcohol and drugs as well as from excessive caffeine consumption.

1. Questioning whether there has been any use of alcohol, psychotropic substances or illicit drugs during the past 24 hours. If yes, the participant is excluded.
2. Questioning if there is a new diagnosis. If yes, the participant will be excluded if the diagnosis meets exclusion criteria.
3. Questions to assess current sleepiness and mood, as this may affect the results of further testing:
 - 3.1 Questions for sleep quality the night before
 - 3.2 Karolinska Sleepiness Scale
 - 3.3 Positive And Negative Affect Schedule (PANAS)
4. Gamma-tACS or controlstimulation (according to randomization) during the following cognitive tests, presented on a computer screen (2 minutes of resting EEG without stimulation after each test):
 - 4.1 Rey Auditory Verbal Learning Test (RAVLT, version 2)
 - 4.2 Letter Fluency; letters F, A, S

- 4.3 Stroop Color and Word Test
- 4.4 Trail Making Test A and B
- 4.5. Word association test; version 2
- 4.6 Four subtests of the Test of Attentional Performance (TAP): Alertness, Go/NoGo, Divided Attention, Visual Scanning
- 4.7 RAVLT delayed recall; version 2
5. Evaluation of side effects with open question (“Did you feel anything particular or note anything special during this session?”)
6. The participant will be given the sleep diary for the third night with the EEG headband.

Visit 6 (day after Visit 5; morning, i.e. start between 8am and 12pm)

1. The participant brings back the EEG-headband (used the night before). Data quality check, review of sleep diary.
2. Questioning whether there has been any use of alcohol, psychotropic substances or illicit drugs during the past 24 hours. If yes, the participant is excluded.
3. Questions to assess current sleepiness and mood, as this may affect the results of further testing:
 - 3.1 Questions for sleep quality the night before
 - 3.2 Karolinska Sleepiness Scale
 - 3.3 Positive And Negative Affect Schedule (PANAS)
4. Cognitive follow-up testing
 - 4.1 RAVLT “ultra-delayed” recall; version 2
 - 4.2 Letter fluency; letters B, H, R
 - 4.3 Stroop Color and Word Test (SCWT)
 - 4.4 Trail Making Test Part A and B
 - 4.5 Word association recall; version 2
 - 4.6 Four subtests of the Test of Attentional Performance (TAP): Alertness, Go/NoGo, Divided Attention, Visual Scanning

Visit 7 (telephone; 5 days after Visit 5)

Performed by telephone.

1. Assessment of adverse events.
2. RAVLT “ultra-delayed” recall.
3. Word association recall; version 2.

